5.7.1. Primary Efficacy Endpoint

The primary efficacy endpoint is the modified erythroid response (mHI-E), defined as below:

- For low transfusion burden (LTB) patients, a hemoglobin increase of ≥ 1.5 g/dL from baseline for ≥ 14 days (in the absence of RBC transfusions). Hemoglobin measurements within 7 days following RBC transfusion will be excluded from analysis.
- For high transfusion burden (HTB) patients, a ≥ 4 units or $\geq 50\%$ reduction in RBC transfusion burden during any rolling 8-week window on treatment compared to baseline. The rolling 8-week window starts on Day 1 and increments by 1 day, e.g., from day 1 to day 56, day 2 to day 57, day 3 to day 58, etc.

A point estimate of the proportion of patients achieving a modified erythroid response will be presented along with its associated exact 95% confidence interval (CI) based on binomial distribution for LTB and HTB patients separately. The complete hemoglobin measurements and RBC transfusion records will be listed for each patient.

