#### 15.2.2. Primary Efficacy Analysis

The **primary efficacy endpoint** is modified erythroid response (mHI-E), defined as the proportion of patients who have a hemoglobin increase of  $\geq$  1.5 g/dL from baseline for  $\geq$  14 days (in the absence of RBC transfusions) in non-transfusion dependent patients, or, a reduction of either  $\geq$  4 units or  $\geq$  50% of units of RBCs transfused over a period of 8 consecutive weeks, compared to the number of units of RBCs transfused in the 8 weeks immediately prior to Cycle 1 Day 1 in transfusion dependent patients (defined as having received  $\geq$  4 units of RBCs within 8 weeks prior to Cycle 1 Day 1). The erythroid response will be summarized using both a point estimate and its exact 95% confidence interval based on binomial distribution. The primary efficacy analysis will be performed using the EE population.

No direct comparison testing with concurrent or historical controls will be performed.

Baseline hemoglobin will be the average of at least two measures (not influenced by transfusion within 7 days of measurement); one measure performed within one day prior to Cycle 1 Day 1 and the other performed 7-28 days prior to Cycle 1 Day 1.

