3.3. Sample Size

There is no formal sample size calculation for the dose escalation portion of the study. A standard dose escalation design will be implemented, and up to 42 patients will be enrolled at up to 7 different dose levels to further evaluate erythroid response.

A sample size of 30 evaluable patients in the expansion cohort will provide approximately 90% power with 1-sided significance level of 0.05 to differentiate an erythroid response rate of 30% from a minimal erythroid response rate of 10% based on Fisher exact test.

A sample size of 25 evaluable patients in each group of expansion cohorts 2 and 3 will provide approximately 80% power with 1-sided significance level of 0.05 to differentiate an erythroid response rate of 30% from a minimal erythroid response rate of 10 % based on Fisher exact test.

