5.2. General Considerations

Unless otherwise noted, continuous data will be summarized with the following descriptive statistics: number of observations (n), mean, standard deviation (STD), minimum, median, and maximum. Categorical data will be summarized with frequencies (n) and percentages (%). In cases where missing data cause percentages not to sum to 100, a missing data row will be provided. Percentages will use column totals as the denominator unless otherwise indicated. For time to event variables, the Kaplan-Meir curves will be presented if the number of patients is more than 5.

All data in the database will be used in the analysis, with the exception of exclusions defined in section 5.7 for efficacy analyses. All study data will be included in study data listings. Missing data will generally not be imputed, unless otherwise stated.

All summaries will be presented by dose cohort, and may also be presented for LTB and HTB patients separately as specified. All summaries will be descriptive. No formal hypothesis testing is planned.

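### The expansion cohorts' power is stated at one-sided 0.05, but the only interval planned for the primary endpoint is a two-sided exact 95% CI, so the stated power does not describe the reported output

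*SAP*

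**What the plan says.** **Sizing.** SAP 3.3 says of the groups in cohorts 2 and 3: "A sample size of 25 evaluable patients in each group of expansion cohorts 2 and 3 will provide approximately 80% power", at a one-sided 0.05 level. For cohort 1 it says: "A sample size of 30 evaluable patients in the expansion cohort will provide approximately 90% power", at the same level. In both cases the aim is to "differentiate an erythroid response rate of 30% from a minimal erythroid response rate of 10" per cent, and the test named is Fisher's exact test. Protocol 15.3 carries the same statements for cohorts 1 and 2.

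**Reporting.** SAP 5.2 states: "No formal hypothesis testing is planned". SAP 5.7 repeats this, and Protocol 15.2.2 rules out comparison testing against concurrent or historical controls. Protocol 15.2.2 adds: "The erythroid response will be summarized using both a point estimate and its exact 95% confidence interval based on binomial distribution". SAP 5.7.1 keeps the point estimate and exact interval but gives "its associated exact 95% confidence interval (CI) based on binomial distribution for LTB and HTB patients separately".

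**Denominators.** SAP 5.7 presents efficacy by dose cohort with LTB and HTB apart, and then lists additional summary groups, among them expansion cohorts 1, 2A, 2B and 3. It does not say whether those additional summaries pool LTB and HTB. SAP 3.1 allows 22 to 28 patients per group of cohort 2 and records that cohort 3 treated 9 patients.

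Neither document gives a responder threshold or says how the interval is to be read against 10%.

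**The concern.** The plan makes a quantitative claim about separating 30% from 10%. With no test planned, the only output from which a reader can judge that claim is the interval in SAP 5.7.1. Its lower limit leaves 2.5% in the tail, whereas the sizing allowed 5%. The stated power therefore belongs to an analysis that is not reported, and the reported interval has a lower chance of excluding 10% than the sizing section suggests.

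There is also a question of unit. Power was stated for whole groups, but SAP 5.7.1 specifies the interval within LTB and HTB. Cohorts 1 and 2B can contain both, so their stratum intervals rest on fewer patients than were sized.

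What is at stake is how a borderline cohort is described. The same count can be said to meet the level used for sizing and also said not to exclude 10%, and nothing written in advance says which description applies.

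**Working it through.** **Inputs.** p0 = 0.10, p1 = 0.30, one-sided 0.05, n = 25 and n = 30 (SAP 3.3); range 22 to 28 (SAP 3.1); exact binomial 95% CI (SAP 5.7.1), taken as two-sided and equal-tailed (Clopper-Pearson).

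**Assumption on the test.** The cohorts are single-arm, so Fisher's test is read as a one-sample exact binomial test. A literal two-sample Fisher test with 25 per arm gives about 45% power and does not reproduce the stated figure.

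**Step 1: reproduce the stated power.** Find the smallest r with P(X ≥ r | n, 0.10) ≤ 0.05. Power is P(X ≥ r | n, 0.30).
- n = 25: P(X ≥ 5 | 0.10) = 0.0980, too large. P(X ≥ 6 | 0.10) = 0.0334, so r = 6. Power = P(X ≥ 6 | 0.30) = 0.8065. This matches the stated 80%.
- n = 30: P(X ≥ 6 | 0.10) = 0.0732, too large. P(X ≥ 7 | 0.10) = 0.0258, so r = 7. Power = 0.8405. This does not match the stated 90%. A one-sided normal approximation without continuity correction gives 90.6%.

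**Step 2: what the reported interval delivers.** The lower limit of an exact two-sided 95% CI exceeds 10% only when P(X ≥ x | n, 0.10) < 0.025.
- n = 25: P(X ≥ 7 | 0.10) = 0.0095, so 7 responders are needed. Probability at 30% = 0.6593.
- n = 30: P(X ≥ 8 | 0.10) = 0.0078, so 8 are needed. Probability at 30% = 0.7186.

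**Step 3: the borderline count.**

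| Result | One-sided p vs 10% | Exact 95% CI | Exact 90% CI |
|---|---|---|---|
| 6/25 | 0.0334 | 9.4% to 45.1% | 11.0% to 42.0% |
| 7/30 | 0.0258 | 9.9% to 42.3% | 11.5% to 39.4% |

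If the true rate is 30%, the probability of exactly 6/25 is 0.8065 − 0.6593 = 0.147. The probability of exactly 7/30 is 0.8405 − 0.7186 = 0.122.

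**Step 4: across the permitted sizes.** The table shows the 95% lower limit at the smallest count that meets one-sided 0.05.

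| n | Count | 95% lower limit | Includes 10%? |
|---|---|---|---|
| 22 | 6 | 10.7% | no |
| 23 | 6 | 10.2% | no |
| 24 | 6 | 9.8% | yes |
| 25 | 6 | 9.4% | yes |
| 26 | 6 | 9.0% | yes |
| 27 | 6 | 8.6% | yes |
| 28 | 7 | 10.7% | no |
| 30 | 7 | 9.9% | yes |

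**Step 5: smaller strata.** As an illustration, assume cohort 1 splits 10 and 20; SAP 3.1 sets a minimum of 10 of each type, if feasible. The 95% CI excludes 10% at 4 or more of 10 (probability 35.0% at a true rate of 30%) and at 6 or more of 20 (58.4%). At n = 10 the one-sided 0.05 rule also needs 4, so that loss comes entirely from the denominator and not from the interval level.

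**The case against.** The strongest reply is that there is no rule to conflict with. The plan is descriptive throughout and names neither a threshold nor a reading of the interval against 10%. Pairing a one-sided phase 2 sizing with a conventional 95% CI is common practice. This stands, and it limits the point to a gap between two statements in the plan.

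A reader might infer that the trial has a faulty test, an inflated false-positive rate, or a success criterion of 6/25 that its own analysis contradicts. The documents support none of these. No test is planned, the 95% CI is the stricter of the two readings, and 6/25 appears nowhere in the text. That count is derived, and only after a one-sample binomial is substituted for the test the plan names. At n = 30 the same substitution does not return the stated 90%, so the count of 7 cannot be traced to the plan's own calculation.

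A reader might also infer that whole-cohort results will never be shown. That goes too far. SAP 5.7 lists the expansion cohorts as additional summary groups and Protocol 15.2.2 does not split the interval, so pooled summaries are arguably planned; the wording leaves it open. Cohort 2A is LTB only, so its interval already covers the group that was sized. Cohort 3, with 9 treated, is far from its sized number whatever interval is used.

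Finally, response data in this open-label trial are reviewed periodically, and the SAP already records end-of-study accrual. Making a more lenient limit the benchmark at this stage would favour borderline cohorts. This objection also stands, and it shapes the fix.

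**Conclusion.** The mismatch is real and narrow. The power in SAP 3.3 is for one-sided 0.05, while the planned interval works at one-sided 0.025. Judged by whether that interval excludes 10%, the probability at a true rate of 30% falls from 80.7% to 65.9% at n = 25 and from 84.1% to 71.9% at n = 30. The difference is a single responder count. It occurs at n = 24 to 27 and n = 30, which includes both target sizes.

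These figures assume a one-sample exact binomial reading of the sizing, a two-sided Clopper-Pearson interval, and a denominator equal to the whole cohort. SAP 4.1 and 5.7 analyse all treated patients rather than evaluable ones, so the actual denominator may not be exactly 25 or 30. The consequence is for how a borderline result is interpreted. It does not make the planned estimate or its interval invalid.

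**What to change.** In SAP 3.3, say that the power is a planning figure at one-sided 0.05. Add that, with the exact 95% CI that will be reported, the probability of excluding 10% when the true rate is 30% is about 66% with 25 patients and 72% with 30. The cohort 1 figure of 90% should be corrected or its method stated in the same edit.

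In SAP 5.7 and 5.7.1, state that the point estimate and exact CI are also given for each expansion cohort as a whole, LTB and HTB together, and keep the LTB and HTB rows. Print the exact 90% CI beside the 95% CI, labelled as descriptive and as matching the level used for sizing in the protocol. State that neither interval is a success criterion.

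The cost is one extra table column, a few sentences, and a stated probability less favourable than the present one. Endpoint, population, sample size and data collection do not change. The wording should be settled before the SAP is signed off ahead of database lock.

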5.7.2. Secondary Efficacy Endpoints

5.7.2.1. RBC Transfusion Independence

For patients with ≥ 2 units of RBC transfusion at baseline, RBC transfusion independence (RBC-TI) response is defined as not requiring RBC transfusion for more than 8 weeks while on treatment.

The proportion of RBC-TI responders will be estimated by a point estimate along with the exact 95% confidence interval based on binomial distribution. The denominator is the number of patients with ≥ 2 units of RBC transfusion at baseline.

Time to RBC-TI will be defined the time from the first dose date to the starting date of the first consecutive 8-week window not requiring RBC transfusion. Duration of RBC-TI will be

calculated as the longest period of time not requiring RBC transfusion during treatment and will be censored at the last record date for ongoing responses.

Both time to and duration of RBC-TI will be analyzed as continuous variables and summarized by descriptive statistics for RBC-TI responders only. Duration of RBC-TI will also be analyzed as a time to event variable using Kaplan-Meier method.

The derivations of RBC-TI response, time to and duration of RBC-TI will be listed for each patient.

5.7.2.2. HI-E Response Rate

Erythroid (HI-E) response will be defined following IWG 2006 criteria.

- For low transfusion burden (LTB) patients, a hemoglobin increase of ≥ 1.5 g/dL from baseline during any rolling 8-week in the absence of transfusion. The rolling 8-week starts and ends at a hemoglobin measurement date with duration $>= 8$ weeks.
- For high transfusion burden (HTB) patients, a reduction by ≥ 4 units of RBC transfusions during any rolling 8-week window on treatment compared to baseline.

A point estimate of the proportion of HI-E responders will be presented along with its associated exact 95% confidence interval based on binomial distribution for LTB and HTB patients separately. HI-E response will also be listed for each patient.

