2. STUDY OBJECTIVES

Primary Objective:

- To evaluate the proportion of patients who have a modified erythroid response (mHI-E), defined as a hemoglobin increase of ≥ 1.5 g/dL from baseline for ≥ 14 days (in the absence of red blood cell [RBC] transfusions) in low transfusion burden patients, or, a reduction of either ≥ 4 units or $\geq 50\%$ of units of RBCs transfused compared to pre-treatment in high transfusion burden patients.

Secondary Objectives:

- To evaluate safety and tolerability of luspatercept (ACE-536)
- To examine rates of erythroid, neutrophil and platelet (HI-E, HI-N and HI-P) responses (International Working Group [IWG] 2006 criteria¹. See Appendix 3)
- To evaluate time to HI-E response and duration of HI-E response
- To evaluate frequency of RBC transfusions in high transfusion burden patients
- To examine the pharmacokinetic (PK) profile of luspatercept
- To examine other pharmacodynamic (PD) effects (e.g., iron metabolism, erythropoietin, reticulocytes, and bone biomarkers)

Exploratory Objectives:

- To evaluate biomarkers related to the TGF- β superfamily
- Evaluation of self-reported quality of life in the expansion cohort using tools including but not limited to the Functional Assessment of Cancer Therapy-Anemia Scale (FACT-An) questionnaire

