5. STATISTICAL METHODOLOGY

5.1. Definitions

Low Transfusion Burden (LTB)

LTB patients are defined as those who received < 4 units of RBCs within 8 weeks prior to Cycle 1 Day 1.

High Transfusion Burden (HTB)

HTB patients are defined as those who required ≥ 4 units of RBCs within 8 weeks prior to Cycle 1 Day 1.

Baseline Hemoglobin

Baseline hemoglobin will be an average of hemoglobin measurements within 28 days of Cycle 1 Day 1, excluding measurements within 7 days following RBC transfusion.

Baseline Transfusion Burden

Baseline transfusion burden will be calculated as the total amount of RBC transfusion during the 8 weeks prior to Cycle 1 day 1.

Baseline for Other Parameters

Baseline erythropoietin (EPO) is defined as the maximum test value within 28 days of Cycle 1 Day 1. For all other parameters, baseline is defined as the last observation on or prior to Cycle 1 Day 1.

End of Treatment (EOT)

Procedures and evaluations for the end of treatment visit should be performed on Day 113 (± 7 days) (28 days after the last dose of ACE-536).

Post Treatment Follow-Up (PTFU)

Procedures and evaluations for the post treatment follow-up visit should be performed on Day 141 (± 7 days) (28 days after EOT visit).

End of Study (EOS)

Procedures and evaluations for the end of study visit should be performed on Day 169 (± 7 days) (56 days after the Day 113/EOT visit).

Patients who discontinue treatment early should complete the end of treatment visit at the time of discontinuation and complete the post-treatment follow-up (PTFU) and EOS follow-up visits 28 days (± 7 days) and 56 days (± 7 days) after the EOT visit.

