7.3. Appendix 3: International Working Group (IWG) Criteria - Erythroid Response Evaluation¹

Hematologic Improvement (HI) ^a	Response Criteria (Responses must last at least 8 weeks)
Erythroid response (Hi-E) (pretreatment Hgb < 11 g/dL)	
Hgb increase of ≥ 1.5 g/dL for patients not transfused; or, as defined by having received less than 4 units of RBCs within 8 weeks of Cycle 1 Day 1
 
Reduction by ≥ 4 units of RBCs transfused (for a Hgb ≤ 9.0 g/dL) during any 8-week period on study, compared with the 8-week period prior to study day 1

Platelet response (HI-P) (pretreatment, $< 100 \times 10^9/L$)	
Absolute increase of $\geq 30 \times 10^9/L$ for patients starting with $> 20 \times 10^9/L$ platelets
 
Increase from $< 20 \times 10^9/L$ to $> 20 \times 10^9/L$ and by at least 100%

Neutrophil response (HI-N) (pretreatment, $< 1.0 \times 10^9/L$)	At least 100% increase and an absolute increase $> 0.5 \times 10^9/L$

^a Pre-treatment counts are averages of at least 2 measurements (not influenced by transfusions) ≥ 1 week apart within 28 days prior to Day 1.

Hgb indicates hemoglobin; RBC: red blood cell; HI: hematologic improvement.

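### HI-N, HI-P and high-transfusion-burden HI-E are labelled IWG 2006, but the SAP's baseline and unit-counting rules differ from its own IWG table (minor)

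*SAP*

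**What the plan says.** Section 2 of the SAP lists a secondary objective, "To examine rates of erythroid, neutrophil and platelet (HI-E, HI-N and HI-P) responses", and points to Appendix 3 for the IWG 2006 criteria. Section 5.7.2.2 repeats the label: "Erythroid (HI-E) response will be defined following IWG 2006 criteria". Section 5.7.2.3 does the same for HI-N and HI-P.

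For high transfusion burden (HTB) patients, section 5.7.2.2 defines HI-E as "a reduction by ≥ 4 units of RBC transfusions during any rolling 8-week window on treatment compared to baseline". Section 5.1 takes the baseline burden as all units in the 8 weeks before Cycle 1 Day 1 (C1D1). Neither these sections nor the general derivation rules in 5.7 filter units by hemoglobin. Appendix 3 has instead "Reduction by ≥ 4 units of RBCs transfused (for a Hgb ≤ 9.0 g/dL) during any 8-week period on study". Its comparator is likewise the eight weeks before treatment starts.

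Section 5.7.2.3 gives no baseline of its own for platelets or neutrophils, so section 5.1 applies: "For all other parameters, baseline is defined as the last observation on or prior to Cycle 1 Day 1". Footnote a of Appendix 3 is attached to the hematologic improvement heading and reads "Pre-treatment counts are averages of at least 2 measurements (not influenced by transfusions"; it also requires them to be at least one week apart and within 28 days before Day 1.

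Section 5.15 has four entries: terminology, time to and duration of mHI-E, the efficacy-evaluable population, and baseline hemoglobin. Neither rule above is among them.

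**The concern.** A rate reported as IWG 2006 will be read as meeting those criteria. Someone who programs the SAP exactly as sections 5.1, 5.7.2.2 and 5.7.2.3 are written will produce HTB HI-E, HI-N and HI-P rates that do not meet the table the SAP itself supplies.

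The baseline rule also has a statistical consequence. One low reading can both admit a patient to the denominator (platelets < 100, ANC < 1.0 × 10⁹/L) and set the value that later counts are compared with. If later counts merely return to the patient's usual level, the patient can be counted as a responder. Averaging two readings weakens this.

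The stake is the labelling and interpretation of secondary endpoints. No test or decision rule depends on them.

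**Working it through.** The documents state no figure to reproduce. The check is a comparison of texts, followed by two illustrations of size.

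**Texts side by side**

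| Item | Rule in SAP body | SAP Appendix 3 |
|---|---|---|
| HTB HI-E, units counted | All (5.1, 5.7.2.2) | For Hgb ≤ 9.0 g/dL |
| Platelet and ANC baseline | Last single value (5.1) | Mean of ≥ 2 values, ≥ 1 week apart, within 28 days |
| HI-N/HI-P duration | Mean over any rolling 8-week window (5.7.2.3) | "Responses must last at least 8 weeks" |

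**HTB HI-E.** Let bl and bh be baseline units given at Hgb ≤ 9.0 and > 9.0 g/dL, and sl and sh the same on study. Appendix 3 does not say whether the qualifier covers baseline units, so both readings are kept.

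- SAP rule: bl + bh − sl − sh ≥ 4.
- Qualifier on both periods: bl − sl ≥ 4.
- Qualifier on study only: bl + bh − sl ≥ 4.

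Example: six baseline units, two of them above 9.0 g/dL, and two on-study units at or below 9.0. The SAP gives 6 − 2 = 4, a responder. The both-periods reading gives 4 − 2 = 2, a non-responder. The on-study-only reading gives 6 − 2 = 4, a responder.

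Now let each count run from 0 to 8 with bl + bh ≥ 4. There are 81 − 10 = 71 baseline pairs. Protocol 10.2.2 discourages on-study transfusion at Hgb ≥ 9 g/dL, so the central case sets sh = 0.

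| Case | Combinations | SAP more lenient / stricter, both periods | SAP more lenient / stricter, on study only |
|---|---|---|---|
| sh = 0 | 71 × 9 = 639 | 260 / 0 | 0 / 0 |
| sh from 0 to 8 | 71 × 81 = 5,751 | 860 / 395 | 0 / 1,875 |

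These are combinations, not patients. They show direction, not frequency. Every case where the SAP rule is stricter needs on-study units above 9.0 g/dL.

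**HI-P and HI-N with no true change.** CV and autocorrelation are assumptions, because the documents give neither. The simulation has 200,000 lognormal patients per setting with first-order autoregressive errors. Pre-treatment values fall on Day −14 and Day 1. On-study hematology is weekly from Day 8 to Day 99, then Days 113 and 141; the last is Day 85 + 56, the cut-off in SAP 5.7. True platelets are uniform on 30–130 with the C1D1 value ≥ 30 (exclusion criterion 6), and true ANC is uniform on 0.3–1.5. A response is any rolling 56-day window whose mean meets the SAP threshold. Entries are false responders, one-value against two-value baseline, accurate to a few tenths of a point.

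| | Autocorr. 0 | 0.5 | 0.8 | 0.9 |
|---|---|---|---|---|
| HI-P, CV 10% | 0.5% v 0.03% | 0.8% v 0.3% | 0.8% v 0.6% | 0.4% v 0.4% |
| HI-P, CV 20% | 11.8% v 5.8% | 14.1% v 9.7% | 13.0% v 11.5% | 9.1% v 8.6% |
| HI-P, CV 30% | 27.1% v 18.4% | 29.9% v 24.5% | 27.2% v 25.5% | 20.6% v 20.2% |
| HI-N, CV 30% | 4.4% v 0.9% | 5.9% v 2.7% | 5.6% v 4.5% | 3.3% v 3.0% |

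HI-N is 0% at CV 10% and about 0.5% at most at CV 20%.

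The single value does not always favor response. With a true platelet rise of 30 and independent errors, it gives HI-P rates of 76%, 78% and 80% at CV 10%, 20% and 30%, against 80%, 81% and 82% with two values. At autocorrelation 0.8 the two baselines differ by 0.3 points or less.

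**The case against.** - **The IWG label imports the missing terms.** On this reading, following IWG 2006 brings in the qualifier and the averaged baseline. But sections 5.1 and 5.7.2.2 state explicit rules that say otherwise, so the SAP would contradict itself and still need reconciling.
- **Section 5.15 has nothing to answer for.** This largely stands. It lists only major changes from Protocol Amendment 6 and does not compare the SAP with its own appendix. The protocol supplied does not appear to be Amendment 6: it has no expansion cohort 3 and plans up to 128 patients, against 153 in the SAP. A reader might infer an undisclosed departure from the governing protocol. The documents cannot show that; they show only a conflict inside the SAP.
- **Protocol 10.2.2 makes the qualifier moot.** It does so for most on-study units, apart from exceptions for symptoms or at the investigator's discretion. It does not govern the eight baseline weeks.
- **The baseline effect is small.** At autocorrelation 0.8 to 0.9 the HI-P difference is at most 27.2 − 25.5 = 1.7 points. Even if all 30 patients of expansion cohort 1 entered the denominator, that is 30 × 0.017 ≈ 0.5 patient. Most of the false-response rate at those autocorrelations remains with two values. This stands, and it keeps the point minor.

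**Conclusion.** The mismatch is established from the SAP alone and needs no outside source. Its numerical effect is not established. For HI-P at CV 20%, the excess of false responders from a one-value baseline runs from 6.0 points (independent errors) to about 0.4 (autocorrelation 0.9). It grows with CV and shrinks as readings become more correlated. For HTB HI-E, the main possible effect is a more lenient rule, if the qualifier is meant to cover baseline units; otherwise there is almost none.

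A reader might go further in three ways that the documents do not support.

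- **HTB HI-E is inflated by a known amount.** Appendix 3 does not fix the scope of the qualifier, and no distribution of units by hemoglobin is given.
- **The 8-week window mean is an error.** It is a permissive but defensible way to apply the duration requirement. A rule that every value must qualify is not clearly better. At CV 20% with a two-value baseline, it cuts HI-P false responders from 5.8% to 0.1% (independent) or from 11.5% to 2.1% (autocorrelation 0.8). But with a true rise of 40 it finds only 29% against 97%, or 58% against 93%.
- **The main efficacy result is touched.** It is not. mHI-E carries no such qualifier, low-burden HI-E uses an averaged hemoglobin baseline, and no formal testing is planned.

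Severity: minor.

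**What to change.** 1. **SAP 5.1 and 5.7.2.3.** Define baseline platelets and ANC as in Appendix 3 footnote a, using the screening and pre-dose C1D1 hematology. State the fallback when only one qualifying value exists.
2. **SAP 5.7.2.2.** Keep the all-units rule for HTB patients, label it *modified IWG 2006* and list it in 5.15. Add the Hgb ≤ 9.0 g/dL version as a sensitivity analysis where pre-transfusion hemoglobin is available. State whether the qualifier covers baseline units and how units with no recorded value are counted.
3. **SAP 5.15.** Note the window mean for HI-N and HI-P as a modification. No sustained-response analysis is needed.

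The cost is minor SAP wording and programming. The hematology is already scheduled. Pre-transfusion hemoglobin is collected for on-study transfusions (Protocol 12.2). Protocol 10.2.2 also draws on documented values from the 12 weeks before C1D1 for transfusion-dependent patients. Historical hemoglobin is collected only where available, so some baseline units may not be classifiable; that is why the qualified version is proposed as a sensitivity analysis. Reported secondary rates may change slightly.
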